### *8.2 Describe any procedures that will be used for quality control of collected data.*

Missing data is the most salient issue with quality of the data. Participants will be asked to complete all questions on the surveys. To reduce attrition in the intervention over time and missing data in the pre- and post-intervention surveys, several strategies will be employed. First, to incentive attendance, compensation will be provided to participants that attend at least 6 intervention sessions and complete the post-intervention surveys. This will be made clear in the consent and assent documents. Second, reminders will be sent the day before each session to remind the participant and their parent about the day and time of the session. Third, to overcome barriers to access, the intervention will be scheduled at a time that is deemed appropriate by the school based on student schedules and the academic calendar. These strategies are in line with previous research on attrition and treatment adherence (Nock & Ferriter, 2005; Snell-Johnson et al., 2004).

### *8.3 Describe the steps that will be taken to secure the data (e.g., information security and privacy training, authorization of access, authentication for access, password protection, encryption, physical and administrative controls, certificates of confidentiality (or "CoC"; see our [CoC link](#)), and separation of identifiers and data) during storage, use, transmission and sharing.*

One dataset that connects names, id numbers, and responses will be stored on a password protected computer. All other data will be identified using a study-specific ID number. For the virtual participants, best practices for telehealth will be followed. A HIPAA-compliant videoconferencing software will be used. The physical address of the participant and the name and phone number of a safety contact will be verified before each session. An alternate phone number will be gathered in case of technology problems. All participants will have access to resources for crisis counseling should the need arise between sessions. Caregivers will have the ability to contact the PI for non-crisis concerns.

### *8.4 Describe how data or specimens will be handled study-wide: e.g.,*

- *Who will extract data or link data/specimens?*
  - Research staff
- *What information will be included in that data or associated with the specimens?*
  - Data include demographic information and responses to survey questions.
- *Where and how data or specimens will be stored?*
  - Data will be collected using Qualtrics then responses will be downloaded and stored on a password-protected OneDrive folder.
- *How long the data or specimens will be stored?*
  - At least 7 years
- *Who will have or otherwise be provided with access to the data or specimens, including for future research or data sharing?*
  - Only the PI, project GA, and post doc will have access to the OneDrive folder.
- *Who is responsible for receipt or transmission of the data or specimens?*
  - PI [name]
- *How will data or specimens will be transported?*
  - Not applicable
- *When will identifiers, linking keys or data be destroyed or disposed.*
  - After all day have been collected and cleaned.

## 9.0 Provisions to Monitor the Data to Ensure the Safety of Subjects

### 9.1 Describe:

- *The plan to periodically evaluate the data collected regarding both harms and benefits to determine whether subjects remain safe. The plan might include establishing a data monitoring committee and a plan for reporting data monitoring committee findings to the IRB and the sponsor.*

A data safety and monitoring plan was developed to ensure that appropriate protocols were in place since children are the primary target population. [name] (PI) will be responsible for all aspects of the project, including design, data collection, and use of data. [name] will be responsible for monitoring data to ensure the safety of participants. Data will be collected at the beginning and end of the study, approximately 10 weeks between data collections. All data will be collected via Qualtrics that only the PI will have access to. Responses will be viewed within 48 hours of survey completion to examine for any distress the participant may express. A descriptive analysis will be conducted as the data come on. At the end of the experimental group, statistical tests will be conducted to ensure that the intervention did not cause excessive distress, particularly we will examine if the internalizing distress score shows an increase of distress more than 10 points on the Tscore scale. If more than 5 participants show an increase in their Tscore for internalizing distress, the waitlist control group will not begin until the team has had a chance to interview the participants to determine if it was the intervention that caused the increase in distress. Unanticipated problems involving risks to participants will be promptly reported to the IRB. The PI will review the progress of the project and data being collected to ensure that potential adverse effects are identified, and if they occur it will be

reported to the IRB. Any action recommended by the IRB to the PI will be implemented immediately.

According to NIH regulations, an adverse event (AE) is drug reaction is also known as a side effect, is any undesirable experience associated with the use of a medicine in a patient. Adverse events can range from mild to severe. Serious adverse events (SAE) are those that can cause disability, are life-threatening, result in hospitalization or death, or are birth defects. There are no components of the intervention that involve medication or other events that are medical in nature, so it is extremely unlikely that disability, life-threatening injuries, hospitalizations, deaths, or birth defects could occur.

Though AE and SAE are very unlikely, since we will be working with minors and the topic of past trauma may come up, there is a chance that a child may report abuse. The research assistants involved in this study are mandated reporters in the State of Florida. Any statements given by children that may be a report of abuse will be documented and the research assistant will report to the PI. If necessary, these reports will be given to the appropriate reporting agency and documented with the IRB.

Additional steps we will take include:

- The investigators will carefully monitor for iatrogenic impacts of the research.
- The PI will ensure that assent (from minors) is obtained prior to performing any research procedures and that all participants are eligible to participate (based on IRB-approved eligibility criteria).
- The investigators will ensure that all study procedures are conducted in strict accordance with the IRB-approved research protocol.
- Additional details are delineated in the Human Subjects section of this grant.

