## **1.0 Procedures Involved**

### *1.1 Describe and explain the study design.*

The study uses a quasi-experimental design with a waitlist control. Youth will be recruited and randomly assigned to either the experimental group or the waitlist control group. At the completion of the experimental group, the waitlist control group will start.

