### *1.2 Provide a description of all research procedures being performed and when they are performed, including procedures being performed to monitor subjects for safety or minimize risks.*

Students will take pre-tests before participating in an 8-week small group therapy. Afterwards, post-tests will be administered and students will be given a chance to provide feedback. A list of the measures is below.

Recruitment will occur by advertising via social media outlets (e.g., Facebook groups targeting local moms) and through local schools. The graphic in the file titled “participants needed” will be posted on social media.

An online survey will be shared with interested caregivers to gauge eligibility. Caregivers will first provide parental consent for their child’s participation, then an eligibility questionnaire will be administered electronically. To be eligible for the study, their child must 1) be a middle or high school student (via caregiver report), 2) have access to a computer with webcam and a private space for each meeting (via caregiver report), and 3) have experienced at least one instance of peer victimization in the past month. The goal is to enroll 6-7 students in the group. Once the group has been enrolled, student assent will be gathered and pre-test surveys will be administered. Participants completing the intervention will be asked to complete the post-test surveys and will be invited to be part of the focus group to gather their feedback.

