**2.0 Study Timelines**

**2.1 Describe:**

- *The duration of an individual subject's participation in the study.*

*10 weeks. One week of data collection before and after the 8 week intervention.*

- *The duration anticipated to enroll all study subjects.*

*Enrollment for the foundation-funded project will occur during September 2023-April 2024.*

*Enrollment for the NIH-funded project will occur during August 2024-May 2025.*

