**3.2 Describe the criteria that define who will be included or excluded in your final study sample.**

No restrictions will be placed on gender or race, though attempts will be made to balance the groups in relation to these demographic characteristics (e.g., avoid groups that have one or two girls and six boys).

To be eligible for the study, the students must 1) be a middle school or high school student (via parent report), 2) have access to a computer with webcam and a private space for each meeting (via parent report), 3) and report distress from victimization by peers that has occurred in the past month

**3.3 Indicate specifically whether you will include or exclude each of the following special populations: (You may not include members of the above populations as subjects in your research unless you indicate this in your inclusion criteria.)**

Individuals who are not yet adults (infants, children, teenagers) will be included in this study.

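### Section 9.1 relies on unnamed statistical tests to ensure no excessive distress, but gives no criterion that could show it, and a non-significant result would not

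*Protocol*

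**What the plan says.** Protocol section 9.1 sets a look at the data when the experimental group finishes and before the waitlist group begins. At that look "statistical tests will be conducted to ensure that the intervention did not cause excessive distress", and in particular the team will see whether the "internalizing distress score shows an increase of distress more than 10 points on the Tscore scale". The text does not say whether the 10 points apply to the group mean or to each participant.

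The action that follows is a count: "If more than 5 participants show an increase in their Tscore for internalizing distress", the waitlist group is held until the team has interviewed participants. No size of increase is attached to the count. The section also provides for survey responses to be viewed within 48 hours and for descriptive analysis as data arrive.

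On numbers, section 1.2 says "The goal is to enroll 6-7 students in the group". Section 1.1 says "Youth will be recruited and randomly assigned to either the experimental group or the waitlist control group", without a ratio. Neither the number of groups per arm nor the total sample is given. The only tests specified anywhere are the repeated measures ANOVAs of Protocol section 8.1 and the SAP. Section 8.1 concedes limited power for the outcome analysis; section 9.1 carries no such caution.

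**The concern.** Section 9.1 gives the tests one job, to establish that harm did not occur. A conventional test is built for the opposite job: it can give evidence of a rise, but failing to find one is not evidence that there was none. The gap is widest in small samples, where a rise as large as the plan's own 10-point mark can easily go undetected. The plan has a margin but no method that compares the data with it.

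At stake is the statement that the team, the ethics board and later readers will take from this look. A true mean worsening of the size the plan calls excessive could be reported as not shown, just before a second set of distressed minors starts the programme.

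**Working it through.** The plan states no power, significance level or SD for this look, so there is no figure of its own to reproduce.

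**Inputs from the documents.** Margin of 10 T-score points and a count of more than 5 (section 9.1); 6-7 in the group (section 1.2).

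**Assumptions.** T-score SD 10; pre-post correlation r of 0.5-0.8; 5% level, two-sided and one-sided; n per arm of 6-7 (one group) or 12-14 (two groups pooled); normal, independent changes.

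**Step 1: SD of change.** SD = 10 × √(2(1 − r)). With r = 0.5 this is 10 × √1.0 = 10.0. With r = 0.8 it is 10 × √0.4 = 6.3.

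**Step 2: chance of missing a true mean rise of 10 points.** Power comes from the noncentral t distribution. For the paired test the noncentrality is (10/SD) × √n on n − 1 degrees of freedom. For the between-arm test on change scores, equivalent to the SAP's time-by-group interaction, it is (10/SD) × √(n/2) on 2n − 2. Example: n = 6, SD 10, paired: √6 = 2.45 against a two-sided critical value of 2.571, giving power 0.51 and a miss rate of 49%.

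| n per arm | SD of change | Paired, two-sided | Paired, one-sided | Between-arm, two-sided | Between-arm, one-sided |
|---|---|---|---|---|---|
| 6 | 6.3 | 13% | 5% | 30% | 18% |
| 6 | 10 | 49% | 32% | 65% | 51% |
| 7 | 6.3 | 7% | 2% | 22% | 12% |
| 7 | 10 | 40% | 25% | 59% | 45% |
| 12 | 10 | 12% | 6% | 35% | 23% |
| 14 | 10 | 7% | 3% | 28% | 18% |

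At n = 12-14 with SD 6.3, the two-sided miss rates are about 0.1% or less (paired) and 2-4% (between-arm).

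**Step 3: what an interval would give.** The one-sided 95% upper limit is the observed mean change plus t × SD/√n within the arm, or the observed difference plus t × SD × √(2/n) between arms.

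- Within arm: the added amount runs from 1.943 × 6.3/√7 = 4.6 points to 2.015 × 10/√6 = 8.2 points.
- Between arms: it runs from 1.782 × 6.3 × √(2/7) = 6.0 points to 1.812 × 10 × √(2/6) = 10.5 points.
- If the true change is zero, the chance that the limit falls below 10 is one minus the one-sided miss rate above: 68-98% within the arm and 49-88% between arms.

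**Step 4: the count.** More than 5 means 6 of 6, or at least 6 of 7. Suppose the true mean rise is 10 points.

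- Read as any increase, each participant's chance is Φ(10/SD): 0.841 at SD 10 and 0.944 at SD 6.3. The count is reached with probability p⁶ = 35-71% at n = 6, and 7p⁶(1 − p) + p⁷ = 69-95% at n = 7.
- Read as an increase above 10 points, each chance is 0.5. The probabilities become 0.5⁶ = 1.6% and 8 × 0.5⁷ = 6.3%.

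The two readings of the same section therefore behave very differently.

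**The case against.** A reader might infer that the plan clears the waitlist group to start on a non-significant p-value. The documents do not say so. Section 9.1 names no test, null hypothesis or threshold, and its reference to an "increase of distress more than 10 points on the Tscore scale" can be read as a check on magnitude. The only stated trigger for holding the waitlist group is the count, backed by interviews, early review of responses and descriptive analysis. This stands: the test is not shown to control the pause.

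A reader might also take 6-7 as the sample at this look. That is an inference from a goal for one group. Section 3.2 says "attempts will be made to balance the groups in relation to these demographic characteristics", in the plural, and section 2.1 adds a second funded period: "Enrollment for the NIH-funded project will occur during August 2024-May 2025". Pooling two groups cuts the miss rates sharply. The question also has one direction, so a one-sided test is defensible, and a high pre-post correlation helps. All of this stands and is why the size is given as a range.

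Finally, it is tempting to say that 6-7 participants can never give reassurance about the mean. Step 3 shows otherwise: an interval within the arm would often exclude a 10-point mean rise when there is no true change. What cannot give that reassurance is a non-significant p-value alone.

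None of this supplies what section 9.1 lacks. The wording still credits tests with establishing absence of harm, and no criterion is stated by which they could.

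**Conclusion.** The point holds in limited form. Section 9.1 asks unspecified tests to support a conclusion that a non-significant result cannot support. If the look covers one group of 6-7, a two-sided test misses a true 10-point mean rise in about 7-49% of trials (paired) or 22-65% (between-arm), and a one-sided test in about 2-32% or 12-51%. With 12-14 per arm the two-sided rates are at most 12% and 35%. These figures rest on an assumed SD of change of 6.3-10 points and a 5% level, neither of which is in the documents, and on a sample size that they do not state.

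The effect is on the claim that distress was not excessive. The stated pause does not depend on the test. Separately, section 9.1 is not consistent within itself or with section 1.2: a rise above 10 points stands beside any increase, and a count above 5 stands beside a group goal of 6-7.

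**What to change.** In section 9.1, delete the wording that a test can ensure no excessive distress. In its place, report on the T-score scale:

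- the mean change in internalizing score in the intervention arm, with a one-sided 95% upper confidence limit read against the plan's own 10-point figure;
- as support, the difference in mean change from the waitlist arm, with the same kind of limit;
- every participant's change;
- the number of participants and groups included. Because section 5.2 deletes the data of terminated participants, the report should also state how many were removed and why.

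The cost is protocol wording; the data are the same. The downside is that the limit, especially between arms, will sometimes be too wide to reassure. The report should then say so.

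Separately, the sponsor must reconcile the 10-point figure with the count of any increase, and the count with the group goal in section 1.2. This point does not propose what the pause rule should be.

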## 5.0 Withdrawal of Subjects

### 5.1 *Describe anticipated circumstances under which subjects will be withdrawn from the research without their consent.*

Subjects will not be withdrawn from the study unless they choose to not complete the survey during the data collection process. Participants may be asked to discontinue if they are too distressed by the topic that it would not be healthy for them to continue.

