### 5.2 *Describe any procedures for orderly termination.*

If subjects are terminated, their data will be deleted and they will not be included in the planned analysis.

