### 5.3 *Describe procedures that will be followed when subjects withdraw from the research, including partial withdrawal from procedures with continued data collection.*

If subjects wish to withdraw, their data will be deleted and they will not be included in the planned analysis.

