Official Title: IVY: Intervention for Victimized Youth

NCT Number: NCT06631274

Document Date: October 18, 2024

Analytic Plan

Analytic Plan

Statistical analyses included three steps. First, missing data occurred only on items measuring social support. Little's test was used to examine the tenability of the assumption of missing completely at random. Second, the mean scores across items in each scale/subscale were computed to represent each intermediate and distal outcome. Third, a series of one-way repeated measures ANOVAs was conducted to examine the impact of intervention, in which participation in the intervention (treatment vs. control) was used as the between-subject factor and time points (time 1 and time 2) was used as the within-subject factor. In addition to significance test for main effect of group, main effect of time, and the interaction effect between time and group, Hedges' g was computed to indicate effect size, where values of 0.2, 0.5, and 0.8 indicate a small, medium, and large effect respectively.

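### The section 9.1 T-score check, which guards the start of the waitlist group, would not count a child who leaves because of distress

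*Protocol*

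**What the plan says.** Protocol section 9.1 sets a safety check at the end of the experimental group: "statistical tests will be conducted to ensure that the intervention did not cause excessive distress". It looks for a rise of more than 10 T-score points in internalizing distress. If more than 5 participants show an increase, the waitlist group waits until the team has interviewed them about the cause. Data are collected only at the beginning and end of the study, about 10 weeks apart.

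Section 5.1 allows for a child leaving because of distress: "Participants may be asked to discontinue if they are too distressed by the topic that it would not be healthy for them to continue". Section 5.2 then says: "If subjects are terminated, their data will be deleted and they will not be included in the planned analysis". Section 5.3 says the same of a child who chooses to leave: "If subjects wish to withdraw, their data will be deleted and they will not be included in the planned analysis".

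Section 1.2 describes who is assessed afterwards: "Participants completing the intervention will be asked to complete the post-test surveys and will be invited to be part of the focus group".

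Section 9.1 also contains general duties without numbers: survey responses are read within 48 hours, the PI reviews progress and reports adverse effects to the IRB, and the investigators watch for iatrogenic effects. It refers to the grant's Human Subjects section for more detail.

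**The concern.** The check exists to show, before a second set of children receives the same intervention, that the first set was not harmed by it. A child asked to stop because the topic was too distressing is one of the most direct signs of such harm that the plan itself foresees, and section 6.1 regards some distress as likely. If the rules on deletion are followed as written, that child leaves no trace in the one numerical result that bears on whether the waitlist group may start. The result would then describe only the children who tolerated the programme.

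**Working it through.** The documents give no figure to reproduce, so the check is to follow one child through the rules and then work out the direction of the effect.

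1. **What a child needs in order to be counted.** The check uses a change, D = post-test T-score minus pre-test T-score. Let C be the number of children counted as showing an increase. More than 5 means C ≥ 6. (The sentence that sets the trigger does not repeat the 10-point limit, so an increase could be read as D > 10 or as D > 0. The argument is the same either way.) A child without both scores has no D.

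2. **How a child can leave for distress.** The team may ask the child to stop (5.1), or the child may withdraw for that reason (5.3; section 6.1 confirms that leaving is free of penalty).

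3. **What then happens to the scores.** Under 5.2 or 5.3 the child's data are deleted. Without the pre-test there is no D, whatever is collected later. This is the firmer of the two routes out of the check. It assumes that a child asked to discontinue under 5.1 counts as terminated under 5.2, and that deletion happens before the check is run. The documents state neither outright, but both are the natural reading.

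4. **The second route.** Section 1.2 describes the post-test for those who complete the intervention. It does not say that nobody else is asked, so this supports step 3 but does not carry the point alone.

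5. **Direction for the count.** Write C(all) = C(stayed) + C(left), where C(left) ≥ 0 is the number of leavers who would have shown an increase. The check sees only C(stayed), so C(stayed) ≤ C(all). Omission can lower the count or leave it unchanged. It cannot raise it.

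6. **Direction for a test on the mean change.** With k leavers among n starters, mean D(all) − mean D(stayed) = (k/n) × [mean D(left) − mean D(stayed)]. This is positive, so the check understates the rise, if those who left for distress would have worsened more than those who stayed. That is an assumption, but a reasonable one for this reason for leaving.

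7. **Size.** Neither k nor n is available: the documents give no exit rate, no arm size and no number of groups. If k = 0 there is no effect at all.

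8. **Other routes by which the exit might reach the waitlist decision.** One leader can work alone with a distressed child (1.3), counselors are available after sessions (6.1), caregivers can reach the PI (8.3), and the PI is a licensed psychologist (15.1). These help the individual child. PI review, IRB reporting and iatrogenic monitoring (9.1) could bring a case to notice. None of them calls for a count of distress exits or ties one to the start of the waitlist group. The interviews in 9.1 are triggered by T-scores alone.

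**The case against.** The strongest reply is that nobody would overlook such a child. The groups are small ("The goal is to enroll 6-7 students in the group"), asking a child to stop is a staff act, and the PI must identify adverse effects and report them. A tally of events already known one by one may add paperwork rather than protection. Section 9.1 also does not expressly exclude these children, and 5.1 can be read as letting a child stop sessions yet still answer the surveys. Full deletion on withdrawal protects minors' privacy. Finally, the grant's Human Subjects section, or a separate monitoring plan, may already require the count.

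Much of this stands. Staff would probably know of a removal and could act on it, and the unseen grant text is a real limit. What remains is that the general duties do not connect such a case to the waitlist decision, and the deletion rules contain no exception that would keep it on record.

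Three stronger readings are tempting but not supported:

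- **That children did leave and were erased.** The SAP's statement that "missing data occurred only on items measuring social support" reads the same whether nobody left or leavers were deleted, so it is evidence of neither.
- **That the study keeps no record of exits anywhere.** Section 8.4 says "Data include demographic information and responses to survey questions", but that list is not exhaustive. It also omits attendance, which payment under 4.1 depends on.
- **That a single exit disables the stopping rule.** In one group of 6 it would, since 6 − 1 = 5 and the trigger needs 6. But the number of groups feeding the check is not stated, and the size of the threshold is a separate question.

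**Conclusion.** The point holds in a limited form. Under the stated rules, a child who leaves because of distress would not enter the only numerical harm check in the supplied documents. If any such exit occurs, the check's count can only err toward looking safe. The size is unknown and may be zero. A before-and-after percentage for a group of 6 or 7 would not measure it either, because the trigger is a raw count without a denominator.

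The conclusion rests on reading 5.2 and 5.3 as covering a child stopped under 5.1, on deletion preceding the check, and on the Human Subjects section not already requiring the count. It does not say that harm went unnoticed or unreported. This is an improvement worth making, not a flaw that undermines the trial. Confidence is medium, mainly because of the text not seen.

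**What to change.** Amend 9.1 along these lines: *The number of children asked to discontinue because of distress, or known to have withdrawn because of it, out of those who started, is recorded. The PI reviews it together with the T-score result before the waitlist group begins, and it is stated beside that result whenever the result is reported.* Amend 5.2 and 5.3 so that this de-identified count survives the deletion of individual data.

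Giving a reason for withdrawal stays voluntary, so the count covers known cases only. Any published count is pooled across groups. The more-than-5 trigger is left as it is. If the Human Subjects section already requires the count, carry that wording into 9.1.

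The cost is a short IRB amendment and probably one line in the consent and assent forms, because the promise of deletion is narrowed slightly. Little new collection is needed: asking a child to stop is a staff act, and attendance must be known because payment requires 6 of 8 sessions. A small risk remains that a single child could be recognised by people in the group. If no child leaves for distress, the only change is that the team can state zero.
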